12.5 Physical Examinations

Physical Examination assessments will be listed for all time points.

12.6 Substance Use

Alcohol intake during the study will be recorded.

12.6.1 Biostatistical Methods

All alcohol intake data collected at scheduled and unscheduled visits will be included in the listings.

The parameter names that will be used in the outputs will comprise the test name and the unit of measure, for example, 'Amount of alcohol consumed (unit)'.

The listings of alcohol intake assessment will include all the information collected.

12.7 Pregnancy Test Results

Pregnancy testing are performed per Schedule of Assessments (refer to the protocol) and any time pregnancy is suspected. A serum pregnancy test is performed at screening and urine pregnancy tests are to be performed thereafter.

All information related to pregnancy testing (urine and serum based - beta-human chorionic gonadotropin) will be listed. This listing will include all pregnancy test results collected during the study.

12.8 Prior and Concomitant Medications

Prior medications are defined as any medication which started and stopped prior to the first dose of study medication.

Concomitant medications are defined as any medication (other than the study drug) that was used at least once after the first administration of the study medication and before end of study. Medications that were stopped on the same date as the first study drug administration will be analyzed as concomitant medications. If a clear determination cannot be made (partial medication end dates) the medication will be classified as concomitant.

Please refer to section 14 for handling of partial dates for medications.

12.8.1 Biostatistical Methods

Concomitant medications will be summarized by ATC class Level 3 and PT. Within each category, the number of subjects who used the medication (count and percentage) will be presented. Subject who used the same medication on multiple occasions will only be counted once in the specific category (PT). PTs will be sorted alphabetically. In addition to the summaries by the coded terms, the number of subjects who used at least one concomitant medication during the study will be presented.

Prior medications will be summarized similarly with concomitant medications.

All information that was collected on the Concomitant Medication eCRF as well as the coded WHO-DD terms will be included in the listings.

All prior and concomitant medications will be listed.

13. ANTIVIRAL ACTIVITY

Antiviral activity endpoints will be analyzed using the Antiviral Analysis Set. All information will be presented by cohort, by study part and overall. All antiviral activity data will be listed by cohort and study part.

13.1 Definition of variables

- Maximum reduction of serum HBsAg from Day 1 until Week 16.
 - Serum \log_{10} HBsAg levels by timepoint
 - Serum \log_{10} HBsAg Nadir level per subject
- Number of subjects with serum HBsAg loss.
- Number of subjects with sustained serum HBsAg loss for ≥ 6 months.
- Number of subjects with anti-HBs seroconversion.
- For HBeAg-positive subjects (Part Two only): number of subjects with HBeAg loss and/or anti-HBe seroconversion.

13.2 Biostatistical methods

All antiviral data collected at scheduled and unscheduled visits will be included in the listings. The results collected as scheduled visits will be included in the summary tables.

The parameter names that will be used in the outputs will comprise the test name and the unit of measure, for example, HBsAg (IU/mL). Parameters will be sorted within parameter class (if present) in alphabetical order within the tables and listings.

Measurements will present summary statistics for the results at the baseline and each scheduled post-baseline visit for each of the parameters. In addition, summaries will be presented for the change from baseline of the antiviral measure to that assessed at baseline values at each scheduled post-baseline visit. See section 3.1 for more detail with regards continuous data representation. Spaghetti plots of \log_{10} -transformed observed values and change from baseline values in HBsAg, HBeAg (Part Two only), CCI [REDACTED] HBV DNA and CCI [REDACTED] will be provided.

Categorical summaries (% of subjects) will present counts and percentages for the reported results at baseline and each post-baseline time point.

14. HANDLING OF MISSING DATA

All data will be analyzed as collected and missing values will not be imputed nor replaced.

Laboratory data that are continuous in nature but are less than the LLOQ or above the upper limit of quantitation will be imputed to the value of the lower or upper limit minus or plus 1 significant digit, respectively (e.g., if the result of a continuous laboratory test is < 30, a value of 29 will be assigned; if the result of a continuous laboratory test is < 30.0, a value of 29.9 will be assigned).

ALGORITHM FOR TREATMENT EMERGENCE OF ADVERSE EVENTS:

START DATE	STOP DATE	ACTION
Known	Known/Partial/ Missing	If start date < study med start date, then not TEAE If start date >= study med start date and start date <= study med end date + 30, then TEAE
Partial, but known components show that it cannot be on or after study med start date	Known/Partial/ Missing	Not TEAE
Partial, could be on or after study med start date OR Missing	Known	If stop date < study med start date, then not TEAE If stop date >= study med start date, then TEAE
	Partial	Impute stop date as latest possible date (i.e. last day of month if day unknown or 31st December if day and month are unknown), then: If stop date < study med start date, then not TEAE If stop date >= study med start date, then TEAE
	Missing	Assumed TEAE

ALGORITHM FOR PRIOR / CONCOMITANT MEDICATIONS:

START DATE	STOP DATE	ACTION
Known	Known	If stop date < study med start date, assign as prior If stop date >= study med start date and start date <= end of study, assign as concomitant
	Partial	Impute stop date as latest possible date (i.e. last day of month if day unknown or 31st December if day and month are unknown), then: If stop date < study med start date, assign as prior If stop date >= study med start date and start date <= end of study, assign as concomitant
	Missing	If stop date is missing could never be assumed a prior medication If start date <= end of study, assign as concomitant
Partial	Known	Impute start date as earliest possible date (i.e. first day of month if day unknown or 1st January if day and month are unknown), then: If stop date < study med start date, assign as prior If stop date >= study med start date and start date <= end of study, assign as concomitant
	Partial	Impute start date as earliest possible date (i.e. first day of month if day unknown or 1st January if day and month are unknown) and impute stop date as latest possible date (i.e. last day of month if day unknown or 31st December if day and month are unknown), then: If stop date < study med start date, assign as prior If stop date >= study med start date and start date <= end of study, assign as concomitant
	Missing	Impute start date as earliest possible date (i.e. first day of month if day unknown or 1st January if day and month are unknown), then: If stop date is missing could never be assumed a prior medication If start date <= end of study, assign as concomitant
Missing	Known	If stop date < study med start date, assign as prior If stop date >= study med start date, assign as concomitant

START DATE	STOP DATE	ACTION
	Partial	Impute stop date as latest possible date (i.e. last day of month if day unknown or 31st December if day and month are unknown), then: If stop date < study med start date, assign as prior If stop date >= study med start date, assign as concomitant
	Missing	Assign as concomitant

Imputed dates will not be presented in the listings.

15. CHANGES TO THE PLANNED ANALYSIS

Not applicable.

16. INTERIM AND FINAL ANALYSIS

16.1 Interim Analysis

No planned interim analysis for this study.

16.2 Final Analysis (End of Study)

After all subjects have completed the study, outstanding data queries have been resolved/closed, and the data have been cleaned and finalized, and database has been locked, the sponsor will authorize breaking of the study blind and the final analysis of the data will be performed.

The final SAP and analysis sets must be approved and signed by the sponsor before the database is locked and treatment assignment unblinded. Any deviations from the planned analysis will be documented in the CSR.

17. SOFTWARE

- The following software will be used to perform the statistical analyses: SAS® Version 9.4 or higher (SAS Institute, Cary, North Carolina, USA).

1. INTRODUCTION

This Statistical Analysis Plan (SAP) provides the outline for the statistical analysis of the pharmacokinetic data collected from the VIR-2218-1005 phase 2 study [REDACTED]. [REDACTED] should be used in conjunction with the separate SAP focusing on safety, tolerability, and antiviral activity of VIR-2218.

The planned analyses identified in this SAP may be included in clinical study reports (CSRs), regulatory submissions, or future manuscripts.

2. PROJECT OVERVIEW

2.1 Study Design

This is a phase 2 randomized, double-blind, placebo-controlled study of VIR-2218 administered subcutaneously to adult subjects with chronic Hepatitis B Virus (HBV) infection without cirrhosis on nucleos(t)ide reverse transcriptase inhibitor (NrtI) therapy. The study is designed to evaluate the safety, tolerability, PK and antiviral activity of VIR-2218.

[figure not shown]
This study will include two Parts:

- Part One: adult subjects with Hepatitis B e-Antigen (HBeAg)-negative chronic HBV infection without cirrhosis on NrtI therapy for \geq 6 months and HBV DNA $<$ 90 IU/mL at screening (by central laboratory)
- Part Two: adult subjects with HBeAg-positive chronic HBV infection without cirrhosis on NrtI therapy for \geq 6 months and HBV DNA $<$ 90 IU/mL at screening (by central laboratory)

Each cohort in Part One/Two will be composed of 5 subjects randomized 4:1 to VIR-2218 or placebo, respectively. There are two planned cohorts (50 mg dose-level and 100 mg dose-level) and 1 optional cohort (\leq 200 mg dose-level) for each of Part One and Part Two of the study. Enrollment of the Part One/Two optional cohorts will be according to the same randomization scheme and eligibility criteria as the Part One/Two planned cohorts. The optional cohorts may be initiated after Safety Review Committee (SRC) review of a minimum of 6 weeks of available safety and antiviral activity data from the 200 mg cohorts of the VIR-2218-1001 regional study.

The estimated total duration for each subject is up to 52 weeks, including screening period (4 weeks), dosing period (4 weeks), post-second dose follow-up period (12 weeks) and extended follow-up period (up to 48 weeks) (Figure 1).

Figure 1. Study Design for Cohorts

2.2 Pharmacokinetic Assessments

Blood samples will be collected to assess concentrations of VIR-2218 and its metabolite (A-312327), as applicable. Timepoints for the collection of samples for VIR-2218 PK analysis of the study are provided Table 1.

Table 1: Part One/Two Pharmacokinetic Assessment Timepoints

Study Day/Week	Protocol Time (Time Window)	PK Blood
Screening		
Day 1	Predose	X ^a
	Dose	
	1 hour ± 5 minutes	X
	2 hours ± 10 minutes	X
	4 hours ± 30 minutes	X
	8 hours ± 30 minutes	X
Day 2	24 hours ± 2 hours	X
Week 1		X
Week 4	Predose	X ^a
	Dose	
	1 hour ± 5 minutes	X
	2 hours ± 10 minutes	X
	4 hours ± 30 minutes	X
	8 hours ± 30 minutes	X
	24 hours ± 2 hours	X
Week 5		X
Week 8		X
Week 16		X
Week 24 ^b		X

^a At ≤ 15 minutes prior to dosing

^b Collected only from subjects in extended follow up.

2.3 Pharmacokinetic Objective

- To characterize the PK of VIR-2218 in subjects with chronic HBV infection without cirrhosis on NrtI therapy.

3. PHARMACOKINETIC EVALUATION/ANALYSIS

3.1 Pharmacokinetic Concentration Population

The pharmacokinetic (PK) concentration population is defined as all randomized subjects who have at least 1 dose of VIR-2218 and at least 1 measurable (>LLOQ) concentration value.

3.2 Pharmacokinetic Analysis Population

The PK Analysis Set includes all randomized subjects who have at least 1 dose of VIR-2218 and 1 post-baseline PK parameter of interests.

3.3 Summary Statistics for PK Data

3.3.1 General Consideration

Due to the short plasma half-life of VIR-2218 and its metabolite (A-312327), pharmacokinetic parameters will be generated separately for day-1 dose and day-29 dose for patients in PK analysis population.

All analyses, including summary for plasma concentration data, summary for plasma PK parameter data, and concentration vs. time plots, will be summarized by Part, Dose Level, and Dosing Day as listed below. In addition, subjects received the same dose level (ie, VIR-2218 50 mg or VIR-2218 100 mg) from Parts One and Two will be pooled together for summary purpose.

- Part One: VIR-2218 50 mg, Day X
- Part One: VIR-2218 100 mg, Day X
- Part Two: VIR-2218 50 mg, Day X
- Part Two: VIR-2218 100 mg, Day X
- Part One & Two: VIR-2218 50 mg, Day X
- Part One & Two: VIR-2218 100 mg, Day X

3.3.2 Summary statistics for plasma concentration data

The concentration and associated unit will be presented as they are received from the analytical laboratories.

The actual sampling date and time and elapsed time relative to dosing time for plasma and urine data will be listed by subject and nominal sampling time, with time deviation (difference in minutes between nominal and actual sampling times) calculated, for all subjects with available concentration data, including subjects excluded from the PK analysis set.

Summary statistics of PK concentration data of VIR-2218 and its metabolite (A-312327) (n, arithmetic mean, standard deviation [SD], coefficient of variation [CV%], geometric mean, geometric CV%, median, minimum and maximum) will be calculated for each time point and summarized by dose day and dose level from each part and in combination (ie, subjects received the same dose level from part one and two will be pooled together), respectively. Geometric CV% calculated as the square root of the exponentiated SD of the natural log transformed data ($\text{SQRT}(\exp(\text{sln}^2) - 1)$, where appropriate.

When reporting individual values and descriptive statistics for VIR-2218 and its metabolite (A-312327) plasma concentration data, the following rules will apply regarding rounding and precision:

- Descriptive statistics for PK concentration data will be reported to the same level of precision as the individual data for the minimum and maximum, and to 1 additional decimal place - for the mean (arithmetic and geometric), median and standard deviation.
- Between-subject CV% and geometric CV% will be reported as a percentage to 1 decimal place.
- Subjects with dosing deviations will be listed but excluded from the summary tables.

3.3.3 *Summary statistics for plasma PK parameters*

MR (metabolite to parent ratio) for a selected PK parameter is defined as the ratio of VIR-2218 metabolite(A-312327) PK parameter divided by the corresponding VIR-2218 PK parameter, for example MR of $AUC_{\text{inf}} (\%) = AUC_{\text{inf}} \text{ of A-312327} / AUC_{\text{inf}} \text{ of VIR-2218} * 100\%$. Summary tables with MR in PK parameters of AUC_{0-8} , AUC_{0-12} , AUC_{inf} and C_{max} will be tabulated.

Calculated PK parameters will be listed and summarized descriptively, including n, arithmetic mean, SD, minimum, median, maximum, coefficient of variation [CV(%)], geometric mean, geometric SD, geometric CV%; For time-related PK parameters (ie., T_{max} , T_{last} and $t_{1/2}$) only n, minimum, median, and maximum will be reported. When reporting individual values and descriptive statistics for PK parameters of VIR-2218 and its metabolite (A-312327), the following rules will apply to rounding and precision:

- Individual values for PK parameters will be reported to 3 significant figures.
- Descriptive statistics for PK parameters will be reported to 3 significant figures.
- Between-subject CV% and geometric CV% will be reported as a percentage to 1 decimal place.
- Data listings containing all documented data and all derived data will be generated. Missing data will not be imputed.
- Subjects with dosing deviations will be reported in the listings but excluded from the summary tables.

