### 4.6. Stopping Rules

The following stopping rules are based on potential safety signals. Standard toxicity grading according to the CTCAE Version 5.0 will be used to grade AEs. When a cohort is stopped, no further study drug will be administered at the dose level and further progression will be suspended. An ad hoc SRC meeting will be held, and only following SRC approval, may dosing be resumed; if required, additional approval from the concerned regulatory authority and the independent ethics committee (IEC)/institutional review board (IRB), in accordance with applicable requirements, will be obtained. De-escalation to a lower dose will be allowed at Sponsor discretion.

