3.4 CONCENTRATION-TIME PROFILES

Individual (for each subject) and mean plasma VIR-2218 and metabolite (A-312327) concentrations will be displayed graphically in linear and semi-logarithmic plots versus time (hour) Part, Dose Level, and Dosing Day 1 and Day 29. The actual collection time will be used for plots of individual plasma concentrations and nominal time will be used for plots of mean plasma concentrations. Below the plots, the number of quantifiable concentrations per timepoint will be displayed. Subjects with dosing deviations will be excluded from the mean plots. They will be displayed in the individual plots with footnote.

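### The PK SAP's dosing-deviation exclusion applies to subjects, not dosing days, so a faulty second dose also removes a valid Day 1 profile from the summaries

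*SAP*

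**What the plan says.** The PK SAP states the exclusion three times.

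- Section 3.3.2, concentration tables: "Subjects with dosing deviations will be listed but excluded from the summary tables".
- Section 3.3.3, parameter tables: "Subjects with dosing deviations will be reported in the listings but excluded from the summary tables".
- Section 3.4, figures: "Subjects with dosing deviations will be excluded from the mean plots". For the individual figures the same section adds: "They will be displayed in the individual plots with footnote".

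None of these sentences limits the exclusion to the dosing day on which the deviation occurred.

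The rest of the PK SAP works by dosing day. Section 3.3.1 gives short plasma half-life as its reason and says that "pharmacokinetic parameters will be generated separately for day-1 dose and day-29 dose for patients in PK analysis population". It then lists every summary by part, dose level and dosing day, and pools the same dose level across the two parts. One dose is enough to enter the population under section 3.2: "The PK Analysis Set includes all randomized subjects who have at least 1 dose of VIR-2218 and 1 post-baseline PK parameter of interests".

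The term dosing deviation is not defined in the PK SAP, the main SAP or the protocol. Main SAP section 6 has important deviations decided before database lock and names investigational product compliance as one category. The PK SAP does not tie its exclusion to that decision.

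**The concern.** The unit of exclusion does not match the unit of analysis. A Day 1 profile is complete weeks before the second dose is due, so an error at the second dose cannot alter it. Even so, the rule as worded takes that profile out of the Day 1 concentration table, the Day 1 parameter table and the Day 1 mean plot.

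The PK SAP is more selective elsewhere. Under section 3.6, when more than 20% of the AUC is extrapolated, only the elimination-related parameters leave the summary statistics, and each excluded value is flagged with an explanation.

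At stake is the descriptive output for a secondary objective, the characterisation of VIR-2218 pharmacokinetics, in groups so small that one subject is a quarter of the data. A programmer following the text literally and one reading it by dosing day would produce different Day 1 tables from the same database.

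**Working it through.** **Group sizes.** PK SAP section 2.1: "Each cohort in Part One/Two will be composed of 5 subjects randomized 4:1 to VIR-2218 or placebo, respectively". That gives 5 × 4/5 = 4 subjects on VIR-2218 per cohort. Pooling the two parts at one dose level (section 3.3.1) gives 2 × 4 = 8. The plan's own total reproduces: 2 parts × 3 cohorts (two planned, one optional) × 5 subjects = 30, as in protocol section 9.8. That figure has no power basis, and the documents give no PK standard deviation and no deviation rate.

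**A subject with a correct Day 1 dose and a partial second dose.**

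| Output | Rule as written | Exclusion by dosing day |
|---|---|---|
| PK Analysis Set | in, through the Day 1 parameters | in |
| Day 1 tables and mean plot | out (n 4 to 3; pooled 8 to 7) | in (n 4; pooled 8) |
| Day 29 tables and mean plot | out (n 3; pooled 7) | out (n 3; pooled 7) |
| Listings, individual plots | in | in |

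The two readings differ only in the Day 1 row. The loss there is 1/4 = 25% of a cohort and 1/8 = 12.5% of a pooled dose level.

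**Illustrative precision.** The PK SAP plans no interval, so this only gives the loss a scale. The 95% t half-width for a mean, in SD units and with the SD held equal, is t(0.975, n−1)/√n.

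- n = 4: 3.182/2 = 1.591
- n = 3: 4.303/1.732 = 2.484; ratio 2.484/1.591 = 1.56
- n = 8: 2.365/2.828 = 0.836
- n = 7: 2.447/2.646 = 0.925; ratio 0.925/0.836 = 1.11

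**How often.** If each subject independently has a second-dose deviation with probability p, a summary of n subjects loses at least one with probability 1 − (1 − p)^n. The values of p are assumptions.

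| Assumed p | Cohort, n = 4 | Pooled, n = 8 |
|---|---|---|
| 5% | 18.5% | 33.7% |
| 10% | 34.4% | 57.0% |
| 20% | 59.0% | 83.2% |

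**Which events can trigger the rule.** A second dose given within the Day 29 ±2 day window (protocol Appendix 2), or withheld under the individual stopping rules (protocol 4.6.2), complies with the protocol. A partial dose, a wrongly missed dose or a dose outside the window would count on an ordinary reading.

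**The case against.** The strongest reply is that section 3.3.1 organises every summary by dosing day, so the team may have meant a subject with a Day 29 deviation to leave the Day 29 summary only. That may well be the intention. But three separate sentences say subjects and none says dosing day, so the text does not deliver it.

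Other points against the concern stand and limit it:

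- Nothing is deleted. Listings and footnoted individual plots keep the data, and with about four subjects per group individual values can be read directly. What is lost is their contribution to n, the means, the CVs and the mean curves.
- Protocol section 4.3 allows replacement after a partial or missed dose, at the same assignment and dose level. The fall from 4 to 3 is therefore not inevitable. Replacement is discretionary, though, and does not clearly cover a full dose given late.
- No interval or test is planned, and the effect on the pooled dose level is small (ratio 1.11).

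A reader might infer two stronger claims, which the documents do not support:

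- *That the loss is informative, because second-dose problems follow liver or tolerability signals.* A dose withheld for those signals under 4.6.2 is protocol-compliant, so it is not an obvious deviation. Nothing in the documents links the remaining events (partial, mistimed or wrongly missed doses) to exposure or tolerability.
- *That a cohort suspension could empty a Day 1 summary.* Protocol 4.6 does say that "only following SRC approval, may dosing be resumed". But all four active subjects would have to be between doses at that moment, all would then have to be dosed outside the window, and a delay under a protocol procedure would have to count as a deviation. No passage establishes any of these conditions.

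**Conclusion.** The concern holds as a point about the unit of exclusion. Followed literally, PK SAP 3.3.2, 3.3.3 and 3.4 drop a valid Day 1 profile from the summaries when only the second dose is at fault, against the plan's own reason for treating the two days separately. Each affected subject costs one of 4 in a cohort and one of 8 in a pooled dose level on Day 1, unless replaced.

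The reach is limited to descriptive secondary PK tables and mean plots. The safety and antiviral analyses are untouched. The conclusion rests on the literal wording and on an ordinary reading of an undefined term. How often it would matter cannot be said from the documents.

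**What to change.** Replace the three sentences in PK SAP 3.3.2, 3.3.3 and 3.4 with one profile-level rule:

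*Concentrations and parameters from a dosing day with a dosing deviation that affects that day's profile are listed and flagged but excluded from the summaries and mean plots for that dosing day only; the subject's other dosing day is retained.*

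Add that, for this PK rule, a second dose withheld or delayed under protocol section 4.6 is not by itself a dosing deviation. Footnote any difference in n between the Day 1 and Day 29 outputs.

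The cost is a few sentences, an exclusion flag by dosing day and a footnote. Whether a deviation affects that day's profile needs a judgement. It should be made and recorded before database lock, alongside the important-deviation decisions in main SAP section 6. No new data are needed, and no dose or clinical rule changes.
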